**Design:**

- This is an open-label, phase I trial with sequential cohorts of patients (3–6 patients per dose cohort) with dose escalation of MVA-brachyury-TRICOM vaccine.
- Three cohorts will receive MVA-brachyury-TRICOM vaccine administered subcutaneously as either 1, 2, or 4 injections of study drug (1 injection =  $2 \times 10^8$  infectious units (IU) at monthly (28 days  $\pm$  4 days) intervals for 3 months (treatment).
- Expansion cohorts of up to 10 patients may be enrolled at the two highest tolerated dose levels. These cohorts will allow certain standard, relatively non-toxic therapies to continue while patients receive vaccine.
- Up to 18 patients may be required to be enrolled in the 3 cohorts, plus an additional 10 at the MTD and at the dose level just below it. Thus, up to 38 patients may be theoretically required to complete this trial. If 3 patients per month can be accrued, the study is expected to require 1 year to complete the necessary enrollment.

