## 2.1.2 Inclusion Criteria (Expansion Phase Only)

The following inclusion criteria apply specifically to patients being considered for the expansion phase of the protocol, as described in Section 8.

*Abbreviated Title: Phase I MVA-Brachyury-TRICOM*

*Version Date: September 14, 2016*

- 2.1.2.1 Subjects with EGFR-mutated lung cancer may continue erlotinib if they have been on the drug for  $\geq 3$  months with stable disease or a response. Erlotinib may also be continued in the case of a progressing tumor after prior response (or  $> 6$  months stable disease).
- 2.1.2.2 Patients with ER+ breast cancer being treated with hormonal therapy (selective estrogen receptor modulator or aromatase inhibitor) who have rising tumor markers as evidence of disease progression or metastatic disease on scans may continue on hormonal therapy while being treated with vaccine.
- 2.1.2.3 Patients with Her2+ breast cancer receiving Her2-directed therapy (e.g. trastuzumab) may continue on that therapy when enrolling into a dose level for which safety has been established.
- 2.1.2.4 Subjects with metastatic colorectal cancer may continue “maintenance” therapy with capecitabine and/or bevacizumab.
- 2.1.3 Exclusion Criteria
  - 2.1.3.1 Concurrent treatment for cancer, with specific exceptions noted in inclusion criteria.
  - 2.1.3.2 Chronic hepatitis B or C infection, because potential immune impairment caused by these disorders may diminish the effectiveness of this immunologic therapy.
  - 2.1.3.3 Any significant disease that, in the opinion of the investigator, may impair the patient’s tolerance of study treatment.
  - 2.1.3.4 Significant dementia, altered mental status, or any psychiatric condition that would prohibit the understanding or rendering of informed consent.
  - 2.1.3.5 Active autoimmune diseases requiring treatment or a history of autoimmune disease that might be stimulated by vaccine treatment. This requirement is due to the potential risks of exacerbating autoimmunity. However, patients with vitiligo or clinically stable autoimmune endocrine disease who are on appropriate replacement therapy (if such therapy is indicated) are eligible.

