### **3 STUDY IMPLEMENTATION**

#### **3.1 STUDY DESIGN**

This is an open-label phase I trial with sequential cohorts of patients (3–6 patients per dose cohort to establish safety) with dose escalation of MVA-brachyury-TRICOM vaccine (see Section 8). Three cohorts will receive MVA-brachyury-TRICOM vaccine administered subcutaneously as either 1, 2, or 4 injections of study drug (1 injection =  $2 \times 10^8$  IU) at monthly (28 days– 4 days up to +14 days) intervals for 3 months (treatment). A dose will be considered missed if not given within 14 days of the original schedule and the patient will resume treatment with the next scheduled dose. The time of patient monitoring post injection would be 2 hour observation after first dose and 30 minutes after subsequent doses.

Toxicity in the 28 days following the first vaccination after the 3rd subject (or 6th subject, if applicable) in dose levels 1 through 3 will be employed for decision-making (i.e., for dose-escalation and for maximum tolerable dose estimation). Inpatient dose escalation will not be allowed. In addition, patients may be enrolled as an expansion cohort at the MTD and at the dose level just below the MTD after either 0 of 3 or no more than 1 of 6 patients have been treated at that dose level and have not experienced a DLT for at least 28 days. Cohorts 2 and 3 will accrue up to an additional 10 evaluable patients each (up to 16 patients total in each) for safety and correlative analysis.

Patients will be sequentially enrolled and monitored for safety as described at dose level 2 and dose level 3. If 0 of 3 or no more than 1 of 6 patients treated at each dose level have experienced a DLT for at least 28 days, we will enroll patients on the expansion phases.

Patients may be concurrently enrolled in the expansion cohort of dose level 2 while enrolling patients on dose level 3 for safety evaluation. Any patient who is eligible will be prioritized into a dose escalation slot. Once all dose escalation slots are filled, patients will be enrolled sequentially onto the expansion phase 2, followed by phase 3. Expansion slots will only be filled by subjects who are not eligible (due to concurrent therapy) for escalation slots until safety is established in both dose level 2 and 3. There will not be randomization.

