## **8 STATISTICAL CONSIDERATIONS**

This study will be conducted as a standard phase I trial with an expanded cohort at the MTD. There are 3 dose levels of vaccine to be evaluated, and initially 3 patients will be enrolled in the lowest dose level. If 0/3 have a dose limiting toxicity (DLT) after 28 days from the third patient receiving the initial vaccine on study, then subsequent patients will be accrued to the next higher dose level. If 1/3 has a DLT, then 3 additional patients will be enrolled at that dose level. If 1/6 has a DLT, escalation may proceed, while if 2+/6 have a DLT, then the MTD will be considered to have been exceeded, and up to 3 additional patients will be enrolled at the next lower dose level if 6 patients have not previously been enrolled at that dose. The MTD will be the dose level at which no greater than 1/6 patients has a DLT, and the next higher dose level has at least 2 patients with a DLT.

The MTD will initially consist of 6 patients as indicated, and the study plans to enroll a total of 10 additional patients each at the MTD and the dose level below MTD (total of 16 at the MTD and up to 16 at the dose level just below the MTD) in an effort to identify significant changes in T-cell precursors will be detectable. Potential evaluation techniques include flow-cytometry based intracellular cytokine staining after bBrachyury 15-mer stimulation and ELISPOT. Evaluations will take place both with respect to absolute change as well as whether a positive response is identified.

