Because we will be using new evaluation techniques with a first in human study, we will enroll 10 patients in an expansion cohort, resulting in 16 potential evaluable patients in the two highest tolerated dose level cohorts, which will provide 80% power to detect a change in T-cell precursors from baseline equal to 1.0 standard deviations of the difference (effect size = 1.0) using a 2-tailed 0.05 alpha level paired t-test. All 10-16 patients in each dose level with evaluable T-cell precursor data at this dose level will be included in the analysis, with 10 patients providing an illustration of 80% power based on that minimal number. The actual power could be greater than 80% if 11-16 patients are evaluable for this determination. In practice, a nonparametric Wilcoxon signed rank test will be used. A positive response using the flow based intracellular cytokine staining assay will be defined as the frequency of T lymphocytes positive for a cytokine or CD107a post-vaccine being increased greater than two-fold compared to both (1) pre-vaccine values and (2) HLA control post-vaccine; the fraction of the patients who have a positive response out of those evaluable for this determination will be noted and reported along with a corresponding 95% confidence interval.

Although the MTD will have been declared after 6 patients at that dose level have been evaluated, monitoring for toxicity in the additional cohort of patients will continue. In the event that more than one third of all patients enrolled at the MTD experience a DLT, protocol modifications will be undertaken to reduce the likely level of toxicity in future patients prior to continuing to enroll additional subjects.

Clinical response evaluation will take place in the patients enrolled at the MTD and the expansion cohort. The results will be considered secondary and will be used to determine the parameters for a subsequent phase II trial should the preliminary findings from this trial warrant further investigation.

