**13.2 APPENDIX B: IMMUNE-RELATED RESPONSE CRITERIA**

Responses will be evaluated in all cohorts to determine eligibility for subsequent cycles, but only responses evaluated in the expanded cohort and in patients enrolled at the MTD will be used for statistical analysis. For the purposes of this study, patients will be re-evaluated for response after day 85 (after 3 doses of vaccine).

Because of direct clinical observations of immune-cell influx into tumor causing tumor enlargement in some patients prior to sustained response, it has recently been suggested that clinical trials involving the use of immunotherapy use alternative guidelines, called immune-related response criteria (irRC), to determine radiographic response or progression after therapy. These recommendations have been used in recent clinical trials. One study of 227 subjects with metastatic melanoma showed that the approximately 10% of patients who had PD by modified WHO criteria but either CR, PR, or SD by irRC had overall survival similar to patients who had SD, PR, or CR by both criteria. The irRC were created using bidimensional measurements (as previously widely used in the WHO criteria). We have taken the concepts of the irRC and combined them with the recently revised RECIST 1.1 to come up with the modified irRC used in this protocol. Consistent with the irRC, the main changes from RECIST 1.1 are (a) a requirement for confirmation of both progression and response by imaging at least 4 weeks after initial imaging and (b) not automatically calling the appearance of new lesions progressive disease if the total measurable tumor burden has not met criteria for progressive disease.

For irRC, only index and measurable new lesions are taken into account. At baseline tumor assessment on this trial, target lesions will be measured along the longest axis and the measurements will be summed, called sum of largest diameter (SLD). These lesions must be a minimum of 10 mm per lesion, maximum of 5 target lesions, maximum of 2 per organ system. At each subsequent tumor assessment, the unidimensional measurement of target lesions and of new measurable lesions is added together to provide the total tumor burden. As per the modified definitions below, all responses and progression except SD require confirmation on a consecutive scan at least 4 weeks from initial observation.

Definitions of irRC:

Response	irRC

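### The clinical response analysis set depends on an MTD that may never be declared; read literally, it drops escalation patients and can leave only expansion patients, who may be on other anticancer therapy

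*Combined protocol and SAP*

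**What the plan says.** **Who is analysed for response.** Section 8 states: "Clinical response evaluation will take place in the patients enrolled at the MTD and the expansion cohort". Appendix B (Section 13.2) makes this exclusive: "only responses evaluated in the expanded cohort and in patients enrolled at the MTD will be used for statistical analysis". Section 6.2 nevertheless requires every patient to be assessed for response. Section 8 calls the response results secondary and says they will inform the parameters of a phase II trial if the findings warrant one.

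**What the MTD is.** Section 8 defines it as a level with no more than 1 of 6 patients having a DLT, "and the next higher dose level has at least 2 patients with a DLT". There are three levels.

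**Which levels are expanded.** Section 8 plans a "total of 16 at the MTD and up to 16 at the dose level just below the MTD". Section 3.1 also refers to the MTD and the level below, but then names fixed levels: "Cohorts 2 and 3 will accrue up to an additional 10 evaluable patients each (up to 16 patients total in each". The schema in Section 3.1.3 gives level 1 only 3 to 6 patients.

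**Who enters the expansion.** The précis says of the expansion cohorts: "These cohorts will allow certain standard, relatively non-toxic therapies to continue while patients receive vaccine". Section 2.1.2 lists erlotinib in EGFR-mutated lung cancer, hormonal therapy in ER+ breast cancer, HER2-directed therapy in HER2+ breast cancer, and capecitabine and/or bevacizumab in colorectal cancer. Section 3.1 adds: "Expansion slots will only be filled by subjects who are not eligible (due to concurrent therapy) for escalation slots until safety is established" at both level 2 and level 3.

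**What is absent.** No section splits response or PFS by concurrent therapy. PFS is named in Section 1.1.2.2, but Section 8 gives it no analysis set.

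**The concern.** The response set is tied to two labels, the MTD and the expansion cohort, instead of to dose level and treatment received. Either label can fail to pick out the patients of interest. If the vaccine is well tolerated, no dose meets the MTD definition, and half of the rule then selects nobody. What remains is the group allowed to stay on other active drugs. The patients left out are escalation patients at the same doses, to whom the expansion-only allowances of Section 2.1.2 do not apply.

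At stake is the reading of activity carried into phase II planning. Stable disease, disease control and PFS are the most exposed. For example, "Subjects with EGFR-mutated lung cancer may continue erlotinib if they have been on the drug for" at least 3 months with stable disease or a response, so disease control on study could reflect that drug. Objective responses are less exposed, because irPR requires a fall of at least 30% from the study baseline. A comparison between levels could also mix dose with background therapy, since the early restriction on expansion slots bears on level 2.

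**Working it through.** **Inputs.** Escalation: 3 to 6 patients per level (Sections 3.1 and 3.1.3). Expansion: up to 10 at each of two levels (précis, Sections 3.1 and 8). The documents give no DLT rate for this vaccine, so rates of 5%, 10% and 20%, the same at every level, are assumed.

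**The plan's own totals.** 3 × 6 + 2 × 10 = 38, and 6 + 10 = 16 per expanded level. Both match the documents. No figure is stated for clinical response.

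**Case A: an MTD is declared and the level below it is expanded.** Under the stated definition this can only be level 2 as MTD with level 1 below.
- Literal set: 16 + 10 = 26.
- All treated at the two levels: 16 + (13 to 16) = 29 to 32.
- Omitted: 3 to 6 escalation patients at the lower level.

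In this same case the expansion passages disagree. Section 8 would expand level 1, while Section 3.1 names cohorts 2 and 3 and Section 3.1.3 keeps level 1 at 3 to 6.

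**Case B: all three levels are tolerated.** Level 3 has no higher level, so no level meets the MTD definition.
- Literal set: 10 + 10 = 20, expansion patients only.
- All treated at levels 2 and 3: 20 + (6 to 12) = 26 to 32.
- Omitted: 6 of 26 (23%) to 12 of 32 (38%).

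**How likely is case B?** Let p be the DLT rate at each level.

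- A level stops at three patients after 0/3 and takes three more only after 1/3: c = (1−p)³ + 3p(1−p)² × (1−p)³.
- Every level is filled to six, which Section 3.1 permits after 0/3: c = (1−p)⁶ + 6p(1−p)⁵.

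The chance that all three levels clear is c³.

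| p | c, stop at 3 | c³ | c, filled to 6 | c³ |
|---|---|---|---|---|
| 5% | 0.973 | 92% | 0.967 | 90% |
| 10% | 0.906 | 74% | 0.886 | 69% |
| 20% | 0.709 | 36% | 0.655 | 28% |

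Sections 1.2.9 and 1.2.14 report no DLTs with the yeast-brachyury vaccine (study of 23 subjects) or with MVA-BN-PRO (24 patients). Low rates are therefore not far-fetched, though those are different products.

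**Concurrent therapy.** The number of expansion patients on it is not stated. The rule in Section 3.1 can require it only in slots filled before both levels are cleared. Level 3 expansion cannot open before level 3 is cleared, so at most the 10 level 2 slots are affected. Later slots are open to patients with or without such therapy.

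**Precision if groups are split.** The exact 95% upper limit with zero responses is 1 − 0.025^(1/n): 46% at n = 6, 26% at n = 12, 17% at n = 20, 13% at n = 26 and 11% at n = 32.

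**The case against.** Several points on the other side are sound.

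- **The endpoint is secondary.** Section 8 sets no response test, threshold or go/no-go rule and names no pooled rate. Safety is the primary objective, and the T-cell set is defined separately by dose level. This stands and limits the weight of the point.
- **A kinder reading exists.** The expanded cohort in Appendix B could mean the whole dose-level cohort, up to 16 patients, in which case nobody at those levels is lost. The précis and Section 8 also refer to the two highest tolerated levels, so the expanded levels can be identified without an MTD. This stands, but neither response passage says that escalation patients count when no MTD is declared.
- **The split is nested in tumour type.** Each therapy in Section 2.1.2 belongs to one tumour type, so with-versus-without therapy is partly a comparison of tumours. This stands and shapes the fix.
- **Escalation patients are not certainly free of other therapy.** Section 2.1.1.11 keeps patients with prostate cancer on GnRH therapy in every cohort, and the exceptions in Section 2.1.1.4 appear under criteria for all subjects. This stands, so patients should be classified by recorded medication.
- **The data can be tabulated later.** True, but Appendix B currently excludes the omitted patients from statistical analysis.

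A reader might infer that concurrent therapy will inflate disease control. The documents do not support that. Section 2.1.2 also admits patients on hormonal therapy with rising markers or metastatic disease on scans, and patients on erlotinib whose tumour is progressing after a prior response. Their disease control could be worse than that of others.

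**Conclusion.** The concern holds in a bounded form. Followed literally, the response rule leaves out 3 to 6 escalation patients at the lower expanded level when an MTD exists. It leaves out 6 to 12 at levels 2 and 3 when all levels are tolerated. The second outcome has a probability of about 90–92%, 69–74% or 28–36% at assumed DLT rates of 5%, 10% or 20%; these figures rest on a common rate at every level. The remaining set, up to 20 patients, may include many or few on active background therapy, so an unsplit stable-disease, disease-control or PFS figure may not describe vaccine alone.

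Two stronger inferences should be resisted. One is that nearly all of the analysed patients will be on other drugs: Section 2.1.2 is permissive, and Section 3.1 restricts only early slots. The other is that only a single expansion cohort at the MTD is meant. The opening sentence of Section 8 suggests it, but the rest of Section 8, Section 3.1 and the précis describe expansion at two levels. No percentage-point bias can be derived from the documents. The primary safety objective and the T-cell power statement are untouched.

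**What to change.** Amend Section 8 and Appendix B (Section 13.2) as follows.

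1. Report response, and PFS where it is reported, by dose level for all treated patients, escalation and expansion together, at each expanded level, whether or not an MTD is declared. Section 8 already defines the T-cell set by dose level.
2. Show results overall and, descriptively, with and without concurrent anticancer therapy as recorded under concomitant medications in the Section 3.3 calendar. List tumour type beside it.
3. Give objective response with exact 95% intervals in patients with measurable disease at baseline. Section 2.1.1.2 also admits nonmeasurable and surgically resected disease, whereas irPR needs a fall in the sum of diameters.
4. Reconcile the passages that define the expanded levels (Sections 3.1, 3.1.3 and 8).

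The cost is wording in the two response passages, the reconciliation of the expansion passages, and some table columns. No new data are needed: Section 6.2 already requires response assessment in everyone. The price is precision. With zero responses, the upper limit is 46% in a group of 6 or 26% in a group of 12, against 17% for a pooled 20, and restriction to measurable disease may shrink the groups further. The split cannot separate vaccine, background-drug and tumour-type effects in an uncontrolled trial, and the tables should say so.

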**Confidential**

*Abbreviated Title: Phase I MVA-Brachyury-TRICOM*

*Version Date: September 14, 2016*

Up to 18 patients may be required to be enrolled in the 3 cohorts, plus an additional 10 at the MTD and the next highest dose level. Thus, up to 38 patients may be theoretically required to complete this trial. If 3 patients per month can be accrued, the study is expected to require 1 year to complete the necessary enrollment.

## **9 COLLABORATIVE AGREEMENTS**

### **9.1 AGREEMENT TYPE**

The MVA-brachyury-TRICOM vaccine is being provided by Bavarian Nordic, Inc. under a Collaborative Research and Development Agreement (CRADA) with LTIB, CCR.

## **10 HUMAN SUBJECTS PROTECTIONS**

### **10.1 RATIONALE FOR SUBJECT SELECTION**

Subjects from all racial/ethnic groups and both genders are eligible for this study if they meet the eligibility criteria. To date, no information suggests that differences in drug metabolism, immune response, or disease response would be expected in one group compared with another. Efforts will be made to extend accrual to a representative population, but in this preliminary study, a balance must be struck between patient safety considerations and limitations on the number of individuals exposed to potentially toxic and/or ineffective treatments on one hand and the need to explore gender and ethnic aspects of clinical research on the other hand. If differences in outcome that correlate with ethnic identity are noted, accrual may be expanded or a follow-up study may be written to investigate those differences more fully.

#### **10.1.1 Inclusion of Women and Minorities**

Both men and women and members of all races and ethnic groups are eligible for this trial.

#### **10.1.2 Exclusions**

Patients with active or chronic infections, including HIV, hepatitis B or C, innate immunodeficiency or autoimmune disease are excluded because this agent requires an intact immune system. In addition, these patients may be at increased risk of complications and side effects due to immunologic changes resulting from this agent.

The effects of yeast-brachyury vaccine on the developing human fetus are unknown. For this reason, women of child-bearing potential and men must agree to use adequate contraception (hormonal or barrier method; abstinence) prior to study entry and for the duration of study participation.

### **10.2 PARTICIPATION OF CHILDREN**

Because no dosing or AE data are currently available on the use of MVA-brachyury-TRICOM vaccine in patients < 18 years of age, children are excluded from this study but may be eligible for future pediatric trials.

